We hypothesize that subjects randomized to receive the KRONOS postoperative unloader knee brace will reach full extension sooner and have reduce extension deficits compared to subjects randomized to receive the standard Breg T-scope hinged brace. In addition, it is hypothesized that the KRONOS subjects will require fewer additional treatments for extensions deficits including, but not limited to, additional therapy, intra-articular injections, oral corticosteroids, manipulation under anesthesia, or arthroscopic revision surgery.

Selection of Subjects –

Patients scheduled to undergo primary ACL reconstruction as indicated via CPT 29888 from the Athena electronic medical record (EMR) will be identified and eligible for enrollment in this study. Following the informed consent process outlined below, we will prospectively enroll and randomize 20 participants to one of the two study arms (KRONOS versus Breg T-scope post-operative knee brace), totaling 40 participants in each group.

Inclusion Criteria:

- Subjects > 18 years of age
- English-speaking
- Scheduled to undergo primary anterior cruciate ligament reconstruction surgery
- No history of prior knee surgery on the operative knee
- No concomitant ligamentous repair or reconstruction procedures (i.e. ligamentous pathology aside from anterior cruciate ligament).
- Subjects undergoing concurrent partial meniscectomy or meniscus repair that would not alter postoperative weight-bearing status or rehabilitation protocol would be eligible for inclusion.

Version 2.0: 4/25/2025 Page 3 of 11

• Clinical and radiographic examination (MRI) consistent with an acute full thickness ACL tear

Exclusion Criteria:

- Age < 18 years of age
- Non-English speaking
- Revision ACL reconstruction
- Multi-ligamentous injury, including concomitant posterior cruciate ligament, medial collateral ligament and fibular collateral ligament injuries
- Concomitant meniscal or cartilage injury that would alter postoperative weight bearing status or rehabilitation protocol
- Inability to comply with the proposed follow-up clinic visits
- Subjects lacking decisional capacity
- Worker's compensation subjects
- Requiring a custom-sized brace

Consent process -

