Potential participants are identified using medical chart and case review. The study eligibility requirements will be reviewed by the PI and study staff. The potential participant is pre-selected as tentatively meeting the eligibility requirements for the study. Research study staff will reach out to eligible patients through a phone call explaining the study. Randomization to the treatment (KRONOS postoperative brace) or control group (Hinged knee brace) will occur at the time of informed consent

Informed Consent Discussion

Investigator and/or PI and research study staff will contact the patient in clinic or via telephone to discuss the research study with them. Ideally, the informed consent discussion should be conducted when the study staff and potential participant has time to ask and answer questions. Information provided to the patient includes the rationale for the study procedure or treatment, the number of study visits and the study activities they will need to complete, risks involved, expected benefits, and alternatives to treatment.

The process may occur over a period of several discussions, culminating in the signing of a consent form in the office (Ipad or paper) or sent to their verified email address. The informed consent discussion will be documented in the patient profile or chart.

If the patient agrees to participate, their email addressed will be verified. The consent will be obtained electronically sent through the secured platform called Patient IQ to their email. The potential subject will then be prompted to reply with the appropriate passcode in order to access the consent form, and then provide the passcode again with their

Version 2.0: 4/25/2025 Page 4 of 11

signature (secured). No research activities will be performed prior to execution of the consent. A copy of the time stamped document will be sent to the study team through the electronic platform and a copy will be sent to the participant.

Study Design & Procedures-

This is a randomized controlled trial.

We estimate 40 participants (20 Kronos: 20 T-Scope) will be enrolled in the study.

Primary outcome variable

• Rates of extension deficit (as measured by the fraction of patients with reduced extension compared to the contralateral knee, determined by heel height and goniometric measurements of knee extension)

Bracing Protocol

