There is no direct benefit to the patient for his/her participation in this study.

The results will contribute to the optimization postoperative bracing and rehabilitation protocols following ACL surgery. This study will help determine if the KRONOS postoperative knee brace is an efficacious and safe methodology to improve range of motion and reduce extension deficits following ACL reconstruction.

Version 2.0: 4/25/2025 Page 8 of 11

Potential risk may include having the participant's privacy or confidentiality compromised. The participant's identities will not be identifiable in publications resulting from this investigation. Every reasonable effort will be made to protect the participant's information while their data is used as part of this study.

The alternative to participation in this study is not to participate.

Costs to the subject—

A brace will be provided to each study participant free of cost regardless of what group they are in—a standard of care Breg T-Scope brace or a Kronos brace.

No insurance coverage will be offered for regularly scheduled standard of care postoperative visits. However, any additional visits scheduled solely for the purpose of this study will be covered at no cost to the patient.

Compensation of subjects-

No compensation will be offered to study participants.

Data Analysis and Statistical Considerations -

Power analysis was based on data published by Mikkelsen et al.⁶ as part of an ACLR randomized controlled trial of a hyperextension brace. A priori power analysis was conducted to determine the sample size required to detect a significant difference in the proportion of patients experiencing a loss of full knee extension of $\geq 2^{\circ}$ between the straight brace and hyperextension brace groups. Using the observed proportions from the study (p1=0.545 for the extension group and p2=0.091 for the hyperextension group), the following parameters were used in G*Power for the calculation: **Statistical test**: Fisher's exact test (two independent groups); **Effect size**: w=0.57; **Significance level** (α): 0.05; **Power** ($1-\beta$): 0.8. The analysis indicated that a total sample size of 32 **participants** (16 per group) would be required to achieve 80% power to detect a statistically significant difference in the proportions of patients experiencing knee extension loss at $\alpha=0.05$. To account for potential loss of subjects to follow-up, a total of 40 subjects will be eligible to be enrolled.

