The statistical software *R* will be used for analyses and calculation of relevant p-values, standard deviation, correlation coefficients, and confidence intervals. Categorical variables will be analyzed via Chi-squared test, while quantitative variables will be analyzed via students' t-test for parametric data and Wilcoxon Mann-Whitney test for nonparametric data.

Data & Safety monitoring

Version 2.0: 4/25/2025

There is minimal risk to the subjects except the potential for loss of privacy and confidentiality, but every reasonable effort will be made to protect the patient's information while their data is used as part of this study.

Data storage & confidentiality –

Participant information will be collected and maintained in a excel data sheet housed on the Midwest Orthopedics at Rush (MOR) server, which is dual-factor authentication protected and accessible only to research staff. Subjects identity will be coded via the use of a separate document key (electronic excel spreadsheet) correlating subjects' Rush medical record numbers with a study ID assigned for the sole purpose of this study. This key electronic document will be maintained as a separate electronic file (excel spreadsheet) from data collection tool and will be housed in the Midwest Orthopaedics at Rush server, which is dual-factor authentication protected and accessible only to research staff.

Files will not be shared with non-study personnel.

According to (Rush policy OP-0432 and CC-G04) and study data must be maintained for 10 years in accordance with Illinois State Law. After this time the data will be destroyed by permanently and securely deleting electronic files on the Master key document (PHI) and the coded data collection tool.

References:

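### The power statement omits sidedness and names a different test from the analysis; under Fisher's exact test, 32 participants give 80% power only one-sided, and w = 0.57 does not match the stated proportions

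*Protocol*

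**What the plan says.** The power analysis is in the Protocol, Data Analysis and Statistical Considerations. It takes its proportions from a published trial of a hyperextension brace: "p1=0.545 for the extension group and p2=0.091 for the hyperextension group". The test is given as Fisher's "exact test (two independent groups"), with effect size w = 0.57, alpha 0.05 and power 0.8. The result is 32 participants ("16 per group) would be required to achieve 80% power to detect a statistically significant difference in the proportions of patients"). No sidedness is given.

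The allowance for attrition follows: "To account for potential loss of subjects to follow-up, a total of 40 subjects will be eligible to be enrolled". No dropout rate is stated; going from 40 to 32 implies a loss of 8, or 20%.

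The next paragraph of the same section sets the analysis: "Categorical variables will be analyzed via Chi-squared test". Fisher's test does not appear there. The primary outcome (Study Design & Procedures) is the fraction of patients with an extension deficit, so the sentence on categorical variables covers it.

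On the total, Study Design & Procedures says "We estimate 40 participants (20 Kronos: 20 T-Scope) will be enrolled in the study", and the Study Summary also gives 40. Selection of Subjects says "totaling 40 participants in each group".

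**The concern.** A power statement should let a reader recover the sample size from its inputs, and the test it assumes should be the one used in the analysis. Neither is so here. The sidedness has to be guessed, the powered test and the planned test differ, and the quoted effect size does not follow from the quoted proportions. The Hypothesis section is directional (it predicts fewer deficits with KRONOS), but the power paragraph speaks of a difference without direction, and a chi-squared test on a 2×2 table is non-directional.

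The figure of 32 matters because the whole attrition allowance rests on it. If 32 evaluable participants really give 80%, the trial can lose 8 of 40. If the true requirement is 38, it can lose 2 with equal groups. Follow-up runs to 12 months, so some loss is plausible.

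**Working it through.** **Inputs** (all from Data Analysis and Statistical Considerations): p1 = 0.545, p2 = 0.091, alpha = 0.05, target power 0.80, 16 per group. The 20:20 allocation is from Study Design & Procedures.

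**Method.** Exact power by full enumeration: sum Bin(x; n1, p1) × Bin(y; n2, p2) over all tables (x, y) whose p-value is at most 0.05.

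**Reproducing the stated 32 with Fisher's test.** One-sided, power is 78.4% at 15 per group and 81.7% at 16. The smallest equal group size is therefore 16, or 32 in total, which matches the protocol. Two-sided, power at 16 per group is 70.9%.

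**Power (%) by test and evaluable participants per group:**

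| Test | 16 | 18 | 19 | 20 |
|---|---|---|---|---|
| Fisher, one-sided | 81.7 | 87.8 | 90.2 | 91.7 |
| Fisher, two-sided | 70.9 | 79.2 | 82.6 | 85.3 |
| Chi-squared, continuity-corrected | 70.2 | 78.9 | 82.2 | 84.0 |
| Chi-squared, uncorrected | 85.5 | 87.9 | 90.2 | 91.7 |

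Two-sided Fisher needs 19 per group, so 38 evaluable. The uncorrected chi-squared test has a maximum type I error of 5.8% at 16 per group, taken over all common proportions.

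**Usual formula for an uncorrected two-sided comparison.** With mean proportion p̄ = (0.545 + 0.091)/2 = 0.318:

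n = [1.960·√(2 × 0.318 × 0.682) + 0.842·√(0.545 × 0.455 + 0.091 × 0.909)]² / 0.454² = (1.291 + 0.484)² / 0.2061 = 15.3, so 16 per group.

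This also gives 32, but it is not the Fisher calculation that the protocol describes.

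**Effect size.** For two equal groups, w = (p1 − p2) / (2·√(p̄(1 − p̄))) = 0.454 / (2 × 0.4657) = 0.487. The stated 0.57 agrees numerically with (p1 − p2)/√(p1 + p2) = 0.454/0.7975 = 0.569, which is not Cohen's w.

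For a 1-df chi-squared test at 80% power, N = (1.960 + 0.842)²/w²:
- w = 0.57: 7.849/0.3249 = 24.2, so N = 25.
- w = 0.487: 7.849/0.2376 = 33.0 (33.03 unrounded), so N = 34.

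Neither value of w leads to 32.

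**Losses from 20:20 under two-sided Fisher, over all splits:**

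| Evaluable | Lowest (%) | Highest (%) |
|---|---|---|
| 39 | 86.5 | 88.9 |
| 38 | 82.6 | 86.6 |
| 37 | 83.1 | 86.8 |
| 36 | 79.2 | 85.0 |
| 32 | 70.9 | 80.4 |

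Any pattern of up to 3 losses leaves at least 82.6%. Four losses, two per group, leave 79.2%.

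**The case against.** The strongest reply is that 32 is adequate under one ordinary reading of the planned analysis. An uncorrected two-sided chi-squared test has 85.5% exact power at 16 per group, and the standard formula for it gives 16 per group. This is correct, and it limits the claim: the need for a one-sided test is specific to Fisher's test. It does not rescue the text, because the protocol attributes its 32 to Fisher's test, and the uncorrected test that supports 32 can exceed the nominal 5%.

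A second reply is that the continuity correction is a detail commonly left to a statistical analysis plan. Taken alone, that is fair. But the powered test, the planned test and w all stand in the protocol and disagree there. A later plan that chose two-sided Fisher would make the protocol's statement of 80% at 32 false, and no later plan can make 0.57 the w for 0.545 against 0.091.

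A third is that the directional hypothesis could justify a one-sided test. It could, but the protocol declares none, and the chi-squared test it plans is not one-sided.

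Finally, the consequence is modest. Enrolment does not change, no dropout rate is given that would make 8 losses expected, and w did not produce the 32. All of this stands and limits the weight of the point.

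**Conclusion.** The concern holds. As described, the calculation is reproduced only by a one-sided Fisher test, which the protocol neither declares nor plans. Two-sided power at 16 per group is 70% to 86%, depending on the test and the continuity correction. Under two-sided Fisher, 38 evaluable participants (19 per group) are needed for 80%, so with equal groups the attrition margin is 2 instead of 8. The stated w of 0.57 is a reporting error; the correct value is 0.49.

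Enrolling 40 remains sound: with 20 evaluable per group, two-sided power is 84.0% (corrected chi-squared), 85.3% (Fisher) or 91.7% (uncorrected chi-squared). These figures rest on the protocol's own proportions and alpha and on rejection at p ≤ 0.05. The point should be fixed, but it does not threaten the design.

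**What to change.** In Data Analysis and Statistical Considerations:

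- State that the primary test is two-sided, and name the same test for the power calculation and the primary analysis.
- If it is Fisher's test, restate power as 85% at 40 evaluable and 71% at 32, with 38 evaluable (19 per group) for at least 80%.
- If it is chi-squared, say whether it is continuity-corrected. With correction, power is 84% at 40 and 70% at 32. Without it, power is 92% at 40 and 86% at 32, with a note that the type I error can reach 5.8% at 16 per group.
- Replace w = 0.57 with 0.49, or delete it.

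In Selection of Subjects, correct the sentence to 20 per group and 40 in total, in line with the Study Summary and Study Design & Procedures.

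The cost is protocol wording only, with no extra participants. If two-sided Fisher or the corrected chi-squared test is chosen, the stated power at 32 completers becomes less favourable.

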- 9. Subjects will undergo standard of care follow up at 1-week, 2-week, 6-weeks, 12-weeks, 6-months, and 12 months. At these standard of care visits, range of motion, including goniometric angle and heel-height measurements, will be made at all postoperative time points.

 Time-to-achievement of full symmetric extension relative to the non-surgical knee will be monitor and recorded. Additional physical exam of the knee will be performed at all follow-up time points.
- 10. At 12 weeks, 6 months, and 12 months, subjects will also be asked to complete standard of care patient reported outcomes questionnaires including IKDC, KOOS, PROMIS, VAS pain, VR/SF 12, and brief resilience scale. Subjects will also be asked to answer standard of care questions regarding return to work and return to sport throughout the 1-year postoperative period.

Retrospective Data Collection

The following data will be abstracted from secured electronic medical record databases (Epic, Athena, Opal, Patient IQ) and electronically recorded on coded data collection tool for this study:

- Demographic information (age, sex, body mass indes (BMI), laterality)
- Chief Complaint
- History of present illness

Version 2.0: 4/25/2025 Page 7 of 11

Physical Exam

Opal and Joints will be used to capture the following:

Surgical approach

Arthroscopic diagnoses

Techniques used

Fixation device / technique

Preoperative imaging including but not limited to MRI

The following outcome variables will be taken from Athena and Patient IQ:

- Postoperative complications
- Failure of primary reconstruction
- Need for a revision or subsequent procedure
- Preoperative / postoperative patient reported outcomes (PRO) including:

IKDC, KOOS, VR-12, PROMIS Depression, PROMIS Physical Function, PROMIS

Pain Interference, Return to Sport (RTS) and Return to Work (RTW), Resilience scale

Other outcomes variables of interest:

- Time-to-achievement of full extension
- Degree of extension loss
- Time to walking without a limp
- Quad circumference difference
- Frequency of brace use
- Number of postoperative physical therapy visits up to one year post-op
- Standard of care Breg T-scope group: time to unlocking the brace
- Kronos group: time to no quad assist (no dial engaged)

Rehabilitation Protocol

The rehabilitation program will be started on the day after surgery according to the providing physician's standard protocol.

Risk/benefit assessment –

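### The chi-squared rule for categorical variables has no small-count exception and no continuity-correction setting, so p-values for sparse secondary outcomes depend on an unstated choice

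*Protocol*

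**What the plan says.** The analysis paragraph of the protocol (Data Analysis and Statistical Considerations) names R as the software and gives one rule for categorical data: "Categorical variables will be analyzed via Chi-squared test". Quantitative variables get a parametric test and a nonparametric alternative in the same sentence. Categorical variables get no alternative, and the continuity correction is not mentioned.

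The rule covers several secondary binary outcomes. The outcome list under Retrospective Data Collection includes postoperative complications, failure of the reconstruction, and "Need for a revision or subsequent procedure". The second hypothesis concerns extra treatments for extension deficits, including "manipulation under anesthesia, or arthroscopic revision surgery".

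On size, Study Design & Procedures states "We estimate 40 participants (20 Kronos: 20 T-Scope) will be enrolled in the study". An exact test is named only in the power paragraph, for the extension-loss proportion: "Fisher's exact test (two independent groups").

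**The concern.** With 20 patients per arm, outcomes such as reoperation or graft failure may produce only a handful of events. The chi-squared approximation is usually not relied on when an expected cell count is below 5, and the corrected and uncorrected versions then differ noticeably. The written rule fits both versions. Two analysts following it could put the same table on opposite sides of 0.05.

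The tables affected would carry the comparison of complications and the reoperation part of the second hypothesis. The primary outcome and the sample size are not at issue here.

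**Working it through.** **Inputs.** 20 per arm (Study Design & Procedures; the study summary also gives a total of 40). Power-paragraph rates 0.545 and 0.091, with 16 per group evaluable. Event rates for the secondary outcomes are not given, so the rates used for them below are assumptions.

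**The plan's own figure.** The pooled two-sided formula, with mean rate (0.545 + 0.091)/2 = 0.318, gives n = [1.960·√(2·0.318·0.682) + 0.842·√(0.545·0.455 + 0.091·0.909)]² / 0.454² = 15.3, so 16 per group as stated. At those rates the smallest expected count for the primary outcome is 0.318·16 = 5.1, or 0.318·20 = 6.4. Both are above 5.

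**When secondary tables are sparse.** With equal arms the smallest expected count is half the total events. It is below 5 when fewer than 10 patients have the event: 10/40 = 25% with 40 patients, 10/32 = 31% with 32. At assumed rates of 5%, 10% and 20% in both arms, the chance of fewer than 10 events among 40 is about 1.00, 0.995 and 0.73.

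**P-values at 20 per arm.** For a events against b:
- Uncorrected X² = 40·(ad − bc)² / (20·20·events·non-events), with c and d the event and non-event counts crossed in the usual 2x2 way.
- The corrected version subtracts 20 (half of 40) from the absolute cross-product difference before squaring.
- Fisher's two-sided p sums the hypergeometric probabilities of tables no more likely than the one observed.

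Worked for 4-0: the cross-product difference is 4·20 − 0·16 = 80. Uncorrected X² = 40·80²/(400·4·36) = 4.44. Corrected X² = 40·60²/57,600 = 2.50. Fisher p = 2·C(20,4)/C(40,4) = 9,690/91,390 = 0.106.

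For 5-0: X² = 40·100²/(400·5·35) = 5.71 and 40·80²/70,000 = 3.66. Fisher p = 2·15,504/658,008 = 0.047.

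| Split | Uncorrected | Corrected (R default) | Fisher |
|---|---|---|---|
| 3-0 | 0.072 | 0.230 | 0.231 |
| 4-0 | 0.035 | 0.114 | 0.106 |
| 5-0 | 0.017 | 0.056 | 0.047 |
| 6-1 | 0.037 | 0.096 | 0.091 |

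At 16 per arm, 4-0 gives 0.033, 0.109 and 0.101. For 4-0 at 20 per arm, the uncorrected p-value is 0.035/0.106, about one third of Fisher's.

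**Type I error at nominal 5%, 20 per arm** (binomial probabilities summed over all tables with p ≤ 0.05):

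| True rate, both arms | Uncorrected | Corrected | Fisher |
|---|---|---|---|
| 5% | 1.2% | 0.03% | 0.2% |
| 10% | 3.9% | 0.4% | 1.2% |
| 20% | 5.0% | 1.8% | 2.3% |

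Over all rates the maximum for the uncorrected test is 5.3% at 20 per arm and 5.8% at 16 per arm. Conditional on the total number of events, the uncorrected test rejects a true null with probability 10.6% for 4 events and 9.1% for 7. For every other total below 10 it is 4.7% or less.

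**Power at assumed rates of 20% and 5%, 20 per arm:** corrected 10.5%, Fisher 16.8%. The uncorrected test and Fisher fall on opposite sides of 0.05 in about 12% of such trials, which puts the uncorrected test at about 29%.

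**The case against.** A reader might infer that a chance 4-0 split in reoperations would be reported as significant. The protocol does not support that. It names R, whose default for 2x2 tables applies the correction and gives 0.114. Only an analyst who switches the default off gets 0.035, and nothing in the protocol says this will be done.

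A reader might also infer that chi-squared p-values here are generally far from the exact ones, or that false positives are inflated. Neither holds. The corrected version tracks Fisher closely, and the uncorrected version keeps an overall size near or below 5%, well below it for very rare events. Its conditional excess is confined to totals of 4 and 7 events.

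Fisher's is not the only exact test. For 4-0 at 20 per arm, Barnard's test gives 0.039 and Boschloo's 0.061, so an unspecified choice among exact tests would reopen the ambiguity. That stands, and it is why the fix must name one test.

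Rarity is assumed. The second hypothesis also counts additional therapy and injections, which need not be rare, so that composite could exceed 10 events.

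Finally, small-count handling is often left to a statistical analysis plan, which is not at hand. That limits the weight of the point. It does not remove it, because the protocol itself fixes one test for all categorical variables and leaves open which version.

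**Conclusion.** The point holds as a minor improvement for secondary outcomes. The written rule leaves sparse 2x2 tables dependent on an unstated correction setting, and neither setting is ideal. Without the correction, the p-value can be about one third of Fisher's. With it, the test is more conservative than Fisher: 5-0 misses 0.05 when Fisher reaches it, and power is 10.5% against 16.8% at the assumed 20% and 5%.

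This rests on 20 per arm and on pooled event rates below 25%, which the protocol neither states nor excludes. The primary outcome at its design rates, the sample size and the overall false-positive rate are unaffected.

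**What to change.** Add to the analysis paragraph: any 2x2 comparison with an expected count below 5 is tested with the two-sided Fisher exact test and reported with the risk difference and its confidence interval; for the remaining chi-squared tests, state whether the continuity correction is applied. Name Fisher's test alone, not an open choice of exact tests. It is the test already named in the power paragraph. With the arm sizes given, the switch depends only on total events, so it can be made without seeing the split between arms.

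The cost is one sentence, with no new data or patients. The downside is that Fisher's test is conservative: its size is at most about 2.3% for event rates up to 20%, and it loses power against the uncorrected test (16.8% against about 29% in the example above). Against R's default corrected test it gains power.
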